INVESTIGATING SOCIAL COMPETENCE IN YOUTH WITH AUTISM: A MULTISITE RCT

PROTOCOL

(CTL+click to jump to section)

CONTENTS

Investigating Social Competence in Youth with Autism: A Multisite RCT	1
Research Components of SENSE Theatre	3
Recruitment	3
EVENTS	3
Recruitment Resources	3
Maintaining Recruitment	3
Recruitment materials	3
INCLUSION/EXCLUSION CRITERIA	4
Scheduling Participants	9
Important Points to make	9
Visit Scheduling	10
Survey Kit	11
Assessment Visit	12
Setup & Consenting	12
Testing	13
Contextual Assessment of Social Skills (CASS)	13
Post-Visits	14
Post-Assessment	14
Testing	14
Post-ERP	14
Post-CASS	15
Follow-Up	15
Forms	15
Follow- Up ERP	15
Follow- Up CASS	16
SENSE Theatre/Tackling Teenage Training Intervention preparation	16
Group Assignment	16
Peers/counselors	16
Training	16
Speakers	16
Binders	16
Food	17
Room	17
Intervention	17

Daily Tasks: -----	17
Online Videos -----	18
Ordering -----	18
Constant Contact (Performance Invites)-----	18
Participant, counselor, and peer certificates-----	18
Post-Intervention -----	19
Sharing contact Info-----	19
National Database for Autism Research (NDAR)-----	20
first steps-----	20
NDAR Data structures/Templates-----	20
NDAR GUIDs-----	20
submitting data to ndar: data validation tool-----	21
NDAR Contacts -----	22
Important Notes about ndar-----	22

RESEARCH COMPONENTS OF SENSE THEATRE

- **Pre Intervention:**
 - **Assessment Visit- research site offices (2-3 hours)**
 - **ERP (45 minutes)**
 - **Contextual Assessment of Social Skills – research site offices (30 minutes)**
- **Intervention (10 week theatre program or 10 week Tackling Teenage Training program)**
- **Post Intervention:**
 - **Assessment Visit (1 hour)**
 - **ERP (45 minutes)**
 - **Contextual Assessment of Social Skills (30 minutes)**
- **Follow-up (3 months after post visit)**
 - **Assessment Visit (1 hour)**
 - **ERP (45 minutes)**
 - **Contextual Assessment of Social Skills (30 minutes)**

RECRUITMENT

EVENTS

- Regional autism community outreach groups (i.e. [Autism Tennessee](#) Conference)
- State Autism Speaks Walk
- Find other events, possible sources of recruitment using regional support groups and awareness programs (i.e. [Tennessee Disability Pathfinder website](#))

To Bring:

- SENSE Theatre mugs, stress balls, flyers, brochures, t-shirts, DVDs, SENSE banner, containers for giveaway items, pens.

RECRUITMENT RESOURCES

- Research Site Website: Coordinate Links and Information with PI and site information technology department
- Vanderbilt Specific Resources:
 - Research Match
 - Study Finder
 - Autism Speaks
 - University Research Notifications
 - www.sensemtheatre.com

MAINTAINING RECRUITMENT

- Maintain ongoing list of interested participants and of peers/counselors.

RECRUITMENT MATERIALS

- [Flyers can be found here](#): Post these in psychiatry, Pediatrics, TRIAD, Developmental Medicine.

- [SENSE Theatre Brochure](#) : Bring to assessments and events.

INCLUSION/EXCLUSION CRITERIA

Inclusion Criteria

This randomized control study will include male and female youth between 10 to 16 years of age. Participants will have a confirmed diagnosis of autism spectrum disorder (ASD) by a clinical psychologist, pediatrician or psychiatrist with expertise in ASD and based on the DSM-V (APA, 2013) and corroborated by the Autism Diagnostic Observation Schedule-Generic (ADOS-G; Lord et al., 1999). Participants whose diagnosis is not confirmed will not be eligible to continue the study. We will recruit participants without confirmed diagnoses but will perform diagnostic testing as described above and if diagnosis is not confirmed participants will not be eligible to continue the study. The ASD group will be high-functioning (intelligence quotient IQ > 70).

In addition to these criteria, a participant must communicate using complete sentences and have fluent speech. If it appears that the participant does not understand some of the verbal or written information, the examiner will use follow-up questions using simple language to ensure the participant understands the purpose and task demands of the study. After clarification, if the participant is unable to demonstrate understanding, respond to questions or willing to complete the questionnaires or protocols, the study team will consult with [name] or the site-PI to determine if the participant should be excluded from the study.

Exclusion Criteria

Youth with ASD and comorbid intellectual impairment will be excluded from the study, as it is unclear if they will comprehend the activities and benefit from the intervention. In order to maintain the safety all participants, youth with current, frequent, and uncontrolled aggression toward other persons or property in the past 6-months will be excluded. This information is obtained during the initial phone screen and during the pre-treatment assessment visit. Participants whose diagnostic testing does not confirm a diagnosis of ASD will not be eligible to continue the study. Additionally, children who are unable to complete significant portions of the research protocol will be excluded. If a participant evidences features of suicidality based on parental report, self-report, or clinical judgement, an immediate referral to Child and Adolescent Psychiatry will be made, and the participant will not be enrolled.

For verbal competence, participants are evaluated for verbal and nonverbal intelligence using the Wechsler Abbreviated Scale of Intelligence (Wechsler, 2nd Edition, 2011). Moreover, the Autism Diagnostic Observation Schedule (ADOS, 2nd Edition; Lord et al., 2012) Module 3 is implemented in the study, which requires participants to have fluent speech. In addition to these criteria, a participant must communicate using complete sentences and have fluent speech. If it appears that the participant does not understand some of the verbal or written information, the examiner will use follow-up questions using simple language to ensure the participant understands the purpose and task demands of the study. After clarification, if the participant is unable to demonstrate understanding, respond to questions or willing to complete the questionnaires or protocols, the study team will consult with [name] or the site-PI to determine if the participant should be excluded from the study.

The Child Depression Inventory (CDI) is a self-report questionnaire consisting of questions related to affective states. Item number 8 explicitly asks, if the child think about or wants to kill him/herself. If a participant endorses this item, it will immediately trigger a response. Specifically, [name] or the lead clinician will be contacted immediately to determine the best course of action (see full crisis plan below).

After enrollment in the study, if the participant endorses suicidal ideation (i.e., endorsing suicidality on item #8 on the Child Depression Inventory), [name] or another study clinician will be contacted immediately to determine the best course of action. Options for addressing the concern may include contacting the participant's outpatient mental health care provider, prompt consultation with pediatric providers within the Department of Psychiatry and Behavioral Sciences, or referral for urgent psychiatric evaluation and treatment. If the threat is determined to not be imminent, the participant may stay enrolled within the study under careful observation. If determined necessary, the parent will be provided with local mental health resources. The clinician will also inform the participant and parent of the importance of going to the Emergency Room should thoughts and feelings intensify. Finally, the participant will be notified that the Principal Investigator may withdraw the participant from the study due to suicidality in order for them to prioritize and receive the necessary care.

List of Mental Health Resources:

Vanderbilt University Medical Center (VUMC)

Vanderbilt Inpatient Hospitalization Program

[contact]

Website: <https://www.vanderbilthealth.com/psychiatrichospital/45262>

Brief Description: We encourage families to join in the treatment process, because family members can have a positive impact on the patient's success. We also provide an aftercare plan to help continue progress after leaving the hospital.

Vanderbilt Adolescent Partial Hospitalization Program

Director: [name]

[contact]

Website: <https://www.vanderbilthealth.com/psychiatrichospital/26600>

Brief Description: This program is designed to care for children, ages 13 to 17, who are dealing with emotional, behavioral and social problems. We offer therapy and medication evaluation services weekdays from 8:00 a.m. to 2:00 p.m. Your child can relax in our warm, therapeutic rooms, and children do not have to stay overnight. We work with parents to provide individualized care for your child, and we see you as an important part of our team.

Vanderbilt Child and Adolescent Outpatient Psychiatry (CAPOC)

Director: [name]

[contact]

Website: <https://www.childrenshospitalvanderbilt.org/service-line/child-and-adolescent-psychiatry>

The following questions will be asked of participants who endorse suicidal ideation. They are derived from the National Institute of Mental Health (NIMH) Ask Suicide Screening Questions.

<https://www.nimh.nih.gov/research/research-conducted-at-nimh/asq-toolkit-materials/asq-tool/asq-screening-tool.shtml>

1. In the past few weeks, have you wished you were dead? Yes No
2. In the past few weeks, have you felt that you or your family would be better off if you were dead? Yes No
3. In the past week, have you been having thoughts about killing yourself? Yes No
4. Have you ever tried to kill yourself? Yes No

If yes, how?

When?

If the patient answers yes to any of the above, ask the following question:

5. Are you having thoughts of killing yourself right now? Yes No

If yes, please describe:

Next steps: If patient answers "No" to all questions 1 through 4, screening is complete (not necessary to ask question #5). No intervention is necessary (*Note: Clinical judgment can always override a negative screen).

If patient answers "Yes" to any of questions 1 through 4, or refuses to answer, they are considered a positive screen. Ask question #5 to assess acuity:

"Yes" to question #5 = acute positive screen (imminent risk identified)

Patient requires a STAT safety/full mental health evaluation. Patient cannot leave until evaluated for safety.

Keep patient in sight. Remove all dangerous objects from room. Alert physician or clinician responsible for patient's care.

"No" to question #5 = non-acute positive screen (potential risk identified)

Patient requires a brief suicide safety assessment to determine if a full mental health evaluation is needed. Patient cannot leave until evaluated for safety.

Alert physician or clinician responsible for patient's care.

SCHEDULING PARTICIPANTS

IMPORTANT POINTS TO MAKE

- Studying peer-mediated effects on social cognition, communication, and interaction through either SENSE Theatre or the Tackling Teenage Training (TTT) program. Assignment to the treatments will be randomly assigned.
- 2 visits required before and after treatment, in addition to follow-up survey.
- Autism
- Ages 10-17
- Does your child use complete sentences to communicate? How are your child's language skills—must have fluent speech/speak in complete sentences.
- Visit breakdown
 - 1: Assessment (about 2-3 hrs.)

- Diagnostic evaluation (ADOS, ask if completed within last 2 years)
 - Estimated IQ (WASI within last year?)
 - Other tasks measuring social perception
- 2: CASS (about 30 Minutes)
 - Interaction in study offices
 - 10 min with other children
 - Videotaped to analyze later
- 3: ERP
 - 45 minutes
 - Watch a social and non-social stimuli and press button in response to stimuli.
 - Wear a mesh hair net type device with tiny sponges.
 - Hair will get slightly damp, but that is the only possible discomfort.
- 4: Intervention
 - 10 consecutive sessions on for both the SENSE Theatre and TTT interventions.
- 5: Performance: Friday and Saturday evening (7:00pm) at end of the SENSE Theatre intervention.
- 6: Post and Follow-up Visits (Assessment, CASS, and ERP).

- Intervention will be free upon completion of all 3 parts (3 visits)
- **Explain randomization:** Your child may be randomly assigned to either the initial study group or an active control group for this study. If your child is assigned to the active control group, you will still complete the study procedures, but will participate in a separate type of intervention program.

VISIT SCHEDULING

General Notes:

- Add each component to Lab Calendar.
- Invite all site's lead investigator and other involved lab members to all scheduled calendar components.
- Give reminder call/email several days before event.

Assessment (2 hours)

- **Establish Days/Times** for when assessments can be scheduled.
- **Room Schedule:** Establish a separate calendar for room reservations. If there are any organizations or individuals that site space must be shared with, ensure those individuals are informed and there are no conflicts for space/scheduling.
- **Reserve Room:** Send email to [the research space coordinators](#) with room you are booking, Date, Times, and project for which the assessment room will be needed.
- **Parking:** Ensure all parking has been reserved for participants upon day and time of their visit.
- **Site Calendar:** Add Assessment to site Lab Calendar (Include Location, subject ID, and who is doing the assessment, in addition to any special notes : first time dx, needs ADOS, does not need ADOS, etc.)

ERP (45 minutes)

- Assessment and ERP are scheduled on the same day for pre-visits.
- Following the assessment, as long as the child meets criteria, give them a 15-30 minute break between assessment and ERP. Time to grab a snack, walk around, etc.
- ERP should be scheduled along the needs and requirements of the site EEG lab performing the ERP task – make sure to have a mutual calendar you can access for the purpose of scheduling appointments.

- ERP visits can be scheduled for 1 hour blocks in green include:
 - SENSE Theatre, id number, and age/sex of participant.
- **Immediately confirm with site EEG team of the scheduled date. Reserve parking**
- **SENSE Calendar:** include ERP, subject id, time, parking spaces reserved.

CASS (30 minutes)

- **Before scheduling CASS** visits you must:
 - (1) Establish with any groups that share research space the times for which you will be using the facilities.
 - (2) Figure out research helper availability, so you may know which research helpers are available when.
 - Do these two things BEFORE scheduling participants!
- **Confirm Research Helpers:** After scheduling a participant, contact available research helpers to confirm their availability.
- **Confirm Research Space:** Then email any groups sharing the research to let them know the date and time you will be using the CASS. Email lab members as needed to schedule space for CASS at the beginning of each week while study is active.
- **Reserve parking** for research helpers AND subject.
- Add CASS visit to **site lab calendar**, including subject id, location, time, research helpers, and reserved parking spaces.

SURVEY KIT

Send to parents before their assessment visit/have parents complete during visit:

- Cover Letter: instructions for questionnaire packet and appointment reminder
- Teacher letter: instructions of teacher questionnaires with deadline.
- Consent & Assent
 - Tell parents to read, but not sign
 - Come with questions
 - We will review and sign at visit
- Photo/Video Release.
- Collect information needed for NDAR
- Directions to the site location, including where to meet
- Medications Checklist
- Short Sensory Profile (SSP)
- Social Communication Questionnaire—Lifetime (SCQ-L)
- ABAS (Parent and Teacher)
- Child Behavior Checklist (CBCL)
- Social Responsiveness Scale-2 (SRS-2, Parent and Teacher)
- Parenting Stress Index Short Form (PSI)
- BRIEF 2
- Conners 3
- MASC-2 Parent Report

- Pubertal Development Scale (PDS)
- Gender Development Survey Parent Report (GDS-Parent)
- Quality of Play Questionnaire (QPQ)

(Parent Surveys: remind them **not** to fill in child's name, DOB, and other identifying information)

Visit 1 (Pre-Test) Only:

****VUMC ONLY:** Due to the unprecedeted situation surrounding the global COVID-19 pandemic, we will, via email, ask currently-enrolled families (only at the VUMC site) from Cohort 4 and 5 (and all future subjects) to complete the following three questionnaires, which relate to stress and coping associated with COVID-19, via REDCap online survey or, if they choose, using physical copies of the questionnaires that we would mail to them:

VUMC ONLY: 1) Compas Responses to Stress Questionnaire (RSQ; Compas, 2020) - COVID-19 Child Self-Report: The RSQ can be filled out by children and adolescents regarding their own personal coping and involuntary stress responses in regards to how they respond to stress related to COVID-19.

VUMC ONLY: 2) Compas Responses to Stress Questionnaire (RSQ; Compas, 2020) - COVID-19 Adult Self-Report: The RSQ can be filled out by parents regarding their own personal coping and involuntary stress responses in regards to how they respond to stress related to COVID-19.

VUMC ONLY: 3) Compas Responses to Stress Questionnaire (RSQ; Compas, 2020) - COVID-19 Parent Report on Child: The RSQ can be filled out by parents regarding their child's coping and involuntary stress responses in regards to how their child responds to stress related to COVID-19.

ASSESSMENT VISIT

SETUP & CONSENTING

- Arrive at the assessment facilities 30 minutes prior to family arrival time.
- Gather appropriate testing materials out of cabinets (ADOS, NEPSY, WASI)
- When the family arrives bring them into a private family room and begin consenting. (15 minutes)
 - Ensure that 2 consent & 2 assent forms are signed by the family and research staff (1 copy for research team & 1 for family)
 - Take the **child's photo** (after parent or guardian has signed Video/Photo Release). Explain that picture will be used during counselor/peer matching.
 - Explain **NDAR** (National Database for Autism Research), and also explain GUID and need for **child's city of birth** in creating unique identifier (see page 14).
- Leave the parent in the family room where they'll wait until the assessment is done with child
 - Retrieve any filled surveys that will be scored later, make sure to check that all files have been answered entirely
- Consenting for Peer Control Group:
 - Peers that are only completing questionnaires and not participating in SENSE Theatre and/or TTT will be provided informed consent forms in person or via email. When conducted by phone, research personnel will review the study process with the parent and then scan or fax the consent form. Once signed/

returned forms are received, the parent and child will be given a link to a REDCap survey to complete questionnaires.

- **Review all questionnaires to confirm they are complete**

TESTING

TASKS

- **The following administration of tests and timelines are normative, but can vary from child to child**

- ADOS - 45 minutes
- NEPSY Memory for Faces - 5 minutes
- WASI Vocab - 12 minutes
- WASI Matrix Reasoning - 8 minutes
- WASI Similarities - 5 minutes
- WASI Block Design - 15 minutes
- NEPSY Memory for Faces Delayed - 3 minutes
- NEPSY Affect Recognition - 7 minutes
- NEPSY Theory of Mind - 7 minutes
- Cohen's Perceived Stress - 5 minutes
- MASC-2 Self Report - 10 minutes
- Gender Development Survey Self Report (GDS-Self) – 5 minutes
- Social Experiences Questionnaire- Self Report (SEQ-S)-- 5 minutes
- Brief Fear of Negative Evaluation-2 (BFNE-2)—5 minutes
- Child Depression Inventory (CDI-2)—5 minutes (If the child endorses item #8 suggesting suicidal ideation, the crisis plan implemented in the Inclusion\Exclusion Criteria section).

CONTEXTUAL ASSESSMENT OF SOCIAL SKILLS (CASS)

- Protocol is based off Ratto et al. (2011).
 - Requires two opposite-sex peers to act as research helpers; one research helper and the participant are led into an observation room (site specific) and told “thank you both so much for coming in. Right now we’d like for each of you to act as if you had recently joined a new club or social group, and now you’re sitting next to each other, waiting for the first meeting of this new club or group to start. You will have 3 minutes to talk to each other, then I will come back in the room.”
 - Research Helper 1 will be the friendly social condition, being supportive and interested in the conversation.
 - Allow for 3 minutes to pass. Record the behaviors that take place during this time for future behavioral coding.
 - Once 3 minutes have passed, remove the research helper from the room. Have participant complete a rating scale while the next research helper is prepared.
 - Research Helper 2 will be the indifferent social condition, they will behave as bored by the conversation and lack social support.
 - Once 3 minutes have passed, remove the research helper from the room.

- Following the completion of the CASS, participants will complete the State-Trait Anxiety Inventory for Children (STAIC) and the Conversation Rating Scale

*Results from the diagnostic and standardized measures and questionnaires will be sent to parents in a brief letter within 6 to 8 weeks of the study assessments.

POST-VISITS

POST-ASSESSMENT

Send to parent/have parent complete at assessment:

- ABAS-3
- PDS
- SSP
- CBCL
- BRIEF-2
- GDS-Parent
- PSI
- Conners- 3
- MASC-2 Parent Report
- QPQ

TESTING

TASKS

- NEPSY Memory for Faces - 5 minutes
- MASC-2 Self Report - 10 minutes
- GDS-Self – 5 minutes
- NEPSY Memory for Faces Delayed - 3 minutes
- NEPSY Affect Recognition - 7 minutes
- NEPSY Theory of Mind - 7 minutes
-
- Cohen's Perceived Stress - 5 minutes
- SEQ-S—5 minutes
- BFNE-2—5 minutes
- CDI-2—5 minutes (If the child endorses item #8 suggesting suicidal ideation, the crisis plan implemented in the Inclusion\Exclusion Criteria section).

POST-ERP

- Protocol for ERP does not change in post-visit.

- ERP may come before Assessment during post-visits.

POST-CASS

- Utilize research helpers unknown to participant (not the same research helpers as pre-CASS)

FOLLOW-UP

FORMS

Send to parent/have parent complete at assessment:

- ABAS-3
- PDS
- SSP
- CBCL
- BRIEF-2
- GDS-Parent
- PSI
- Conner's 3
- MASC-2 Parent Report
- QPQ

Tasks include:

- NEPSY Memory for Faces - 5 minutes
- MASC-2 Self Report - 10 minutes
- Gender Development Survey Self Report – 5 minutes
- NEPSY Memory for Faces Delayed - 3 minutes
- NEPSY Affect Recognition - 7 minutes
- NEPSY Theory of Mind - 7 minutes
- Cohen's Perceived Stress - 5 minutes
- SEQ—5 minutes
- BFNE—5 minutes
- CDI—5 minutes (If the child endorses item #8 suggesting suicidal ideation, the crisis plan implemented in the Inclusion\Exclusion Criteria section).

All forms must be completed by same rater in Pre and Post (i.e. same teachers and same parent/guardian)!

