***Follow-Up forms sent to both Experimental and Control groups approximately 8 weeks after post-visits.**

FOLLOW- UP ERP

- Protocol for ERP does not change in follow-up visit.
- ERP may come before Assessment during follow-up

FOLLOW- UP CASS

- Utilize research helpers unknown to participant (not the same research helpers as in the pre and post- CASS)

SENSE THEATRE/TACKLING TEENAGE TRAINING INTERVENTION PREPARATION

GROUP ASSIGNMENT

- Once randomization into SENSE Theatre or TTT is complete and participants have been assigned to groups, send letters to families informing them of what group they are assigned.
- Send out RedCap survey which collects information regarding Medication (see if there have been any changes), food allergies, behavioral information, t-shirt size.
- Add participant and research helper contacts to a designated lab cell phone

PEERS/COUNSELORS

- **Application:** Interested peers and counselors will complete an application
- **Decisions:** Lead site investigator, and theatre director will narrow down who is to be interviewed for a peer and counselor position.
- **Background checks:** all adults participating in the intervention (18 years +) must have an existing background check with Vanderbilt or go through the process of getting one.
- **Protection of Minors Training:** Make sure all counselors and peers are compliant with the site's requirements for protections of minors training. Contact site IRB for "Research Involving Minors" for more information pertinent to site requirements.
- **Consent and Video Release Forms:** sent to peers/counselors participating in intervention.
- **Intervention Information:** Send training schedule, location map, and first days schedule (via email), and an email reminder 1 week before training begins.

TRAINING

SPEAKERS

- Site PI will be responsible for contacting and choosing speakers.
- Coordinate who will be presenting when, 6 weeks before intervention begins.
 - Research Assistant/Coordinator—"Introduction to Autism"
 - Confidentiality & Code of Conduct, SENSE Theatre Manual, SENSE Lab & Theatre, Behavioral Strategies.
- Copies of past presentations can be provided to any sites by the SENSE Research Coordinator.

BINDERS

- Binder Materials:
 - Binder Covers (Color)
 - Binder spine labels (color)

- Divider Tab Labels
- Presentations (Black and White)
- Schedule
- Music/Lyrics (SENSE Theatre Intervention only)
- Name Tags
- Pre/Post Test
- SENSE Theatre Manual (Black and White)

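### The script for explaining randomization ranks the two arms by label, which gives parents an avoidable expectancy cue for any post-treatment parent-rated SRS

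*Protocol*

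**What the plan says.** **Script.** Protocol, Scheduling Participants, Important Points to Make, describes the trial to families twice. The first bullet says that effects are studied "through either SENSE Theatre or the Tackling Teenage Training (TTT) program" and refers to both as treatments. The bullet on explaining randomization says "Your child may be randomly assigned to either the initial study group or an active control group for this study", and adds that a child in the control group "will participate in a separate type of intervention program".

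**Surrounding cues.** The giveaways, banner and brochure under Recruitment carry the SENSE Theatre name, and the instruction for the brochure is "Bring to assessments and events". The talking points also mention evening performances, for the SENSE Theatre arm only.

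**Sequence.** The Survey Kit is headed "Send to parents before their assessment visit/have parents complete during visit" and includes "Social Responsiveness Scale-2 (SRS-2, Parent and Teacher" forms. Under Group Assignment, once randomization is complete, staff "send letters to families informing them of what group they are assigned". The follow-up section adds: "All forms must be completed by same rater in Pre and Post (i.e. same teachers and same parent/guardian".

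**Use of the outcome.** The SAP tests growth in the SRS and CASS in Hyp 2.1 and uses both again in the mediation test, Hyp 2.2. Its power section names memory for faces as the primary dependent variable. Neither document describes masking of parents or teachers, a measure of expectancy, or which SRS form is analyzed.

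**The concern.** An active comparator is useful partly because it evens out attention and expectation between the arms. Labels that present one arm as the study and the other as its control work against that. A parent who knows the child's arm, and has worked out which program is the comparator, may rate change more or less generously for that reason alone. An EXP versus ACC difference on a parent-rated SRS would then mix treatment effect with expectation, and the mediation path to SRS growth would carry the same mixture.

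Parents cannot be masked to the program their child attends, so some of this risk is unavoidable. The part the script adds is avoidable.

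**Working it through.** No figure in the plan bears on expectancy, so there is none to reproduce. The check is mainly a comparison of passages, followed by one sensitivity calculation.

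**1. The two descriptions.** The opening bullet names both programs and ranks neither. The randomization bullet names neither program and ranks the arms. They describe the same allocation in the same list, so the neutral wording already exists in the Protocol.

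**2. Can a parent tell which program is the comparator?** Not from the sentence itself. The inference is easy from its surroundings: the branded materials, and a performance attached to one arm only.

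**3. When can the label act differently in the two arms?** All families hear the same script at scheduling, before the baseline forms. The order of the Protocol implies that allocation follows the pre-visits, though it does not say so outright. On that order, any shift the label causes at baseline has the same expectation in both arms, so the expected between-arm difference is 0. A difference can arise only after the allocation letter, at post and follow-up.

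**4. Which outcomes are exposed?**

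| Outcome | Rated or produced by | Exposure to this cue |
|---|---|---|
| SRS, parent form | Parent who heard the script and knows the arm | Direct, if collected after treatment |
| SRS, teacher form | Teacher; nothing shows that teachers hear the script | Less |
| CASS | Recorded for later behavioral coding; masking of coders not stated | Less |
| Memory for faces (primary) | Performance test and ERP | Less |

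**5. Is the parent SRS scheduled after treatment?** The SRS-2 is in the pre-visit Survey Kit. It is not in the parent form lists under Post-Assessment or Follow-Up. The SAP's growth model needs it at pre, post and follow-up. The exposure in step 4 therefore depends on a collection that the SAP implies and the Protocol does not list.

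**6. How sensitive is a test to rating bias?** Inputs: 216 participants (SAP, power section); 108 per arm (assumed 1:1, since no ratio is given); SD 1; no true effect; two-sided 5% z-test of an endpoint difference; total between-arm rating bias of b SD (assumed). Repeated measures and clustering are ignored.

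P(reject) = Φ(b/√(2/n) − 1.96) + Φ(−b/√(2/n) − 1.96), with √(2/108) = 0.136.

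| b | b/0.136 | P(reject) |
|---|---|---|
| 0 | 0 | 5.0% |
| 0.05 | 0.37 | 6.6% |
| 0.10 | 0.73 | 11.4% |
| 0.20 | 1.47 | 31.2% |
| 0.25 | 1.84 | 45.1% |

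The last row sets b at the SAP's threshold for a clinically important difference. The table shows how a given total bias, from any source, would affect such a test. It does not estimate b, and it does not say how much of b the script causes.

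**The case against.** The strongest case against is that the wording's own effect cannot be isolated. Parents will know the program attended, and the branding and performance would remain after any rewrite. This stands. It limits what the fix can achieve and rules out attaching a size to the script.

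Four stronger readings are tempting and are not supported:

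- **That parents are told which program is the comparator, or which one is expected to work.** The sentence names neither program and says nothing about expected benefit. Parents have to infer the first point, and the opening bullet is neutral.
- **That hearing the label before baseline biases the comparison.** All families hear it, and allocation appears to come later, so it cannot by itself separate the arms at baseline.
- **That the bias can be sized against the SAP's effect sizes.** An assumed .05 to .15 SD would be .05/.25 = 20% to .15/.25 = 60% of the clinically important d, but the assumption has no source in the documents. It would also describe expectancy as a whole, not the script's share.
- **That family letters and flyers carry the same labels, or that disappointment will raise dropout in one arm.** No letter or flyer text is shown. The reference to experimental and control groups in the follow-up section is an instruction to staff. Consent pages are not available, so their wording cannot be judged, and nothing in the documents bears on differential dropout.

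None of this defends the labels themselves: they serve no purpose that the neutral wording in the same list would not serve as well.

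**Conclusion.** The point holds as an inexpensive improvement to wording. The script uses ranked labels where the Protocol elsewhere uses neutral ones. This gives an avoidable expectancy cue to parents who later learn their arm and may then rate an outcome named in Hyp 2.1 and Hyp 2.2. The documents do not show that bias is present.

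The size is unknown. The exposure is confined mainly to the parent form of a non-primary outcome. The conclusion assumes that staff follow the script as written, that the parent SRS is collected after treatment as the SAP implies, and that the parent form enters the analysis, which the SAP does not specify. If only the teacher form is analyzed, the concern largely falls away.

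The absence of the SRS from the post and follow-up lists is a separate inconsistency and the firmer of the two.

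**What to change.** 1. Replace the randomization bullet with wording in line with the opening bullet, for example: *Your child will be randomly assigned to one of two 10-session programs, SENSE Theatre or Tackling Teenage Training. Both are being studied, and all families complete the same study visits.*
2. Avoid control-type and initial-group labels in anything said or sent to families.
3. Record the date of the change by cohort.
4. Separately, reconcile the Post-Assessment and Follow-Up form lists with the SAP's growth model for the SRS.

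Useful additions are to name the SRS form analyzed, to state whether teachers and CASS coders are masked, and to record parent expectancy once allocation is disclosed.

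**Cost.** Items 1 to 3 need a wording change, with a minor ethics amendment if the script is an approved document. The downside is that cohorts already enrolled will have heard the present script, so the wording will differ between cohorts; the recorded date lets this be described. Item 4 is an edit if the SRS is already being collected, and otherwise adds a form to two visits. Recording expectancy would add a short item for parents.
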